Investigating Barriers for Decision Making in a Danish Breast Cancer Screening Context

Statistical Analysis Plan

NCT05444725

Unique Protocol ID: 2016-051-000001, 2563

Date: August 23, 2022

Statistical analysis plan

Introduction

Informed decision making and the use of decision aids are often recommended in breast cancer screening. However, informed decision making might be challenged by *ex ante* positive attitudes towards screening. Several studies have found high levels of enthusiasm towards screening including one of our own studies in a Danish breast cancer screening context (unpublished). Therefore, we will investigate preferences and attitudes towards breast cancer screening, invitation, and decision making among Danish women in this study. The study will be conducted by sending out an online questionnaire to women aged 44-49 in Denmark. Women will be randomized to one of three versions of the questionnaires: 1) Questionnaire with "Stage of Decision Making"-question to investigate women's decision making process regarding participation in screening (by asking whether women have made their decision about participation or not based on six different options of decision stages), 2) Questionnaire with choice framing (presentation of a choice between participation in breast cancer screening or no screening), or 3) Questionnaire with opportunity framing (only presentation of screening, no alternative) to investigate the decision making process and the impact of different framing. Next, women are asked to state their intended participation in screening on a 5-point Likert scale.

Subsequently, questionnaire data will be linked to register data on sociodemographic factors from Statistics Denmark.

The following variables are available:

- Register data: educational level, socioeconomic status (based on employment), civil status, municipality, and whether the person was immigrant, descendant (born in Denmark by foreign parents) or of Danish origin.

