- Questionnaire: age, educational level, previous breast cancer, perceived risk of breast cancer, breast cancer worry, breast cancer among family/friends, previous mammogram, intended participation (and stage of decision making for one of three groups), reading health information in general, having read the leaflet about breast cancer screening (link in the invitation letter to this study), being more positive/negative about screening after having read breast cancer screening information, being more/less willing to participate after having read breast cancer screening information, indicating that screening participation is their very own decision vs. indicating that you should follow recommendations from health authorities about screening participation (two questions), indicating that they prefer to make their own decision about screening participation based on own attitudes and values and the information available vs. indicating that they prefer that health authorities recommend whether they should participate or not (two questions), and preferences for future screening invitation.

Hypothesis and aims

Main hypothesis: The majority of Danish women have made the decision about breast cancer screening participation prior to invitation and presentation of screening information. More specifically, the main hypothesis for this study is that 80% of Danish women have already made their decision when presented to the opportunity framing and 70% when presented to the choice framing.

To investigate the main hypothesis above, the following analyses will be performed, where subheadings indicate the theme addressed by the analyses:

Screening decision made prior to reading information

- Estimate prevalence of women who have made the decision to participate in breast cancer screening across randomization groups and for each of the two framings. Intended participation is answered on 5-point Likert scale and will be dichotomized as participation (two categories) and non-participation/unsure (three categories).
- Compare prevalence of women who have made the decision depending on opportunity vs. choice framing with chi-squared test.

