- Crude and adjusted* logistic regression with intended participation as outcome and framing as independent categorical variable. The group receiving “Stage of decision making” is included in this analysis for comparison. Intended participation is answered on 5-point Likert scale and will be dichotomized as participation (two categories) and non-participation/unsure (three categories).
- Sensitivity analyses restricting intended participation to only one category for all analyses (only “Yes, I want to participate” and not “I think I want to participate”).

Stage of decision making

- Estimate prevalence of women in each decision stage based on “Stage of decision making”.
- Crude and adjusted* logistic regression with intended participation as outcome and “Stage of decision making” as independent continuous variable.

Aim 1: Women do not take the presented screening information into account when making their decision about participation.

To investigate aim 1, the following analyses will be performed, where subheadings indicate the theme addressed by the analyses:

Different framing

- Same analyses as for main hypothesis – does framing make a difference (and is information taken into account)?

Do women read health information

- Estimate prevalence of women who read health information in general and who have read the breast cancer screening information specifically.
- Crude and adjusted* logistic regression with participation as outcome and reading information (in general + screening related) as independent variables.

More or less positive/negative after reading information

- Estimate prevalence of women who are more or less positive/negative depending on previously intended participation and framing, respectively.

- Crude and adjusted* logistic regression with more or less positive/negative as outcome and intended participation and framing as categorical independent variables.

Dichotomization of outcome depends on results**

More or less willing to participate after reading information

- Estimate prevalence of women who are more or less willing to participate depending on previously intended participation and framing, respectively.
- Crude and adjusted* logistic regression with more/less willing as outcome and intended participation and framing as categorical independent variables.

Dichotomization of outcome depends on results**

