Aim 2: Women think of the screening participation as less of an actual (individual) choice and more of something to comply with when invited.

To investigate aim 2, the following analyses will be performed:

- Estimate prevalence for each of the two statements (indicating that screening participation is their very own decision vs. indicating that you should follow recommendations from health authorities about screening participation) for all five categories (5-point Likert scale, "strongly agree" – "strongly disagree").
- 2x2 table of seeing it as individual choice vs. recommendation to comply with ("strongly agree" and "agree" for both statements).
- Crude and adjusted* logistic regression with thoughts on screening participation as outcome and intended participation and framing as categorical independent variables.

Thoughts on screening participation is a dichotomized variable based on the two statements mentioned above. Women are categorized as "individual choice" when they answer "agree" or "strongly agree" to the first statement and answer "neutral", "disagree", or "strongly disagree" to the other statement (coded 0). In contrast, women are categorized as "recommendation to comply with" when they answer "agree" or "strongly agree" to the second statement and answer "neutral", "disagree", or "strongly disagree" to the other statement (coded 1). Inconsistent responses to the two statements and disagreement towards both statements are coded as missing and their frequency reported.

Aim 3: Women do not want to make an informed decision about their own health (and be responsible for their own health).

To investigate aim 3, the following analyses will be performed:

- Estimate prevalence for each of the two statements (indicating that they prefer to make their own decision about screening participation based on own attitudes and values and the information available vs. indicating that they prefer that health authorities recommend whether they should participate or not) for all five categories (5-point Likert scale, "strongly agree" – "strongly disagree").
- 2x2 table of wanting informed decision making vs. health authorities make recommendation ("strongly agree" and "agree" for both statements).

- Crude and adjusted* logistic regression with preference for decision making as outcome and intended participation and framing as categorical independent variables.

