Preference for decision making is a dichotomized variable based on the two statements mentioned above. Women are categorized as “wanting informed decision making” when they answer “agree” or “strongly agree” to the first statement and answer “neutral”, “disagree”, or “strongly disagree” to the other statement (coded 0). In contrast, women are categorized as “health authorities make recommendation” when they answer “agree” or “strongly agree” to the second statement and answer “neutral”, “disagree”, or “strongly disagree” to the other statement (coded 1). Inconsistent responses to the two statements and disagreement towards both statements are coded as missing and their frequency reported.

At the very end of the questionnaire, women are asked about their preferences for future screening invitation (how and what material is sent at invitation regarding invitation letter, information leaflet and pre-scheduled time for screening). For this question, four pre-defined options are suggested based on the current Danish invitation strategy and, lastly, a text field is provided for other suggestions and thoughts. Based on these responses, prevalences can be estimated for the four pre-defined invitation strategies. Next, responses provided in the text field can be investigated and possible themes and other strategies can be identified. This can be important knowledge for future research and administration of the Danish breast cancer screening program.

* The following variables are used as independent variables in adjusted analyses: educational level, socioeconomic status (based on employment), civil status, whether the person was immigrant, descendant (born in Denmark by foreign parents) or of Danish origin, perceived risk of breast cancer, breast cancer worry, and previous mammogram.

** Because women are generally very positive about screening and want to participate in screening, we hypothesize that it is more likely that women will be more negative and less willing to participate after reading screening information than becoming even more positive and more willing. This is because we assume that it is difficult to be much more positive and more willing to participate than is already the case.

If this hypothesis is true, the responses will be dichotomized as follows:

Positive/negative: Focus is on women being more negative, therefore, the two “negative” responses will be coded as 1 and the two “positive” responses and “unchanged” will be coded as 0.

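### Breast cancer among family/friends is collected but left out of the only covariate list, so adjusted odds ratios for non-randomised exposures may keep some residual bias; adding it is a minor, free improvement

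*SAP*

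**What the plan says.** The Introduction's list of questionnaire variables has the item in the middle of the risk-related questions: "breast cancer worry, breast cancer among family/friends, previous mammogram, intended participation".

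The single-asterisk footnote, placed after Aim 3, is the only definition of adjustment in the SAP. The covariates are those "used as independent variables in adjusted analyses: educational level, socioeconomic status (based on employment), civil status", then origin (immigrant, descendant or Danish), and finally "perceived risk of breast cancer, breast cancer worry, and previous mammogram". The family/friends item is not among them. The SAP gives no reason and names no other use for it.

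The same footnote serves models of two kinds.

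- **Randomised exposure.** Framing is assigned by design: "Women will be randomized to one of three versions of the questionnaires".
- **Non-randomised exposures.** These are:
  - decision stage, under the main hypothesis: "logistic regression with intended participation as outcome and “Stage of decision making” as independent continuous variable";
  - reading, under Aim 1: "Crude and adjusted* logistic regression with participation as outcome and reading information (in general + screening related) as independent variables";
  - intended participation, under Aim 2: "thoughts on screening participation as outcome and intended participation and framing as categorical independent variables". The Aim 1 models for changed attitude and changed willingness, and the Aim 3 model, have the same form.

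**The concern.** For the second kind of model, the covariate list is the only protection against background differences. Knowing someone with breast cancer normally predates the questionnaire, and no leaflet can change it. It could plausibly influence both how a woman engages with information or decides, and what she says about taking part. It is therefore a natural candidate for adjustment, and the data are already in hand.

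Two mechanisms are possible.

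1. **Residual confounding.** Family/friends history is associated with the exposure and also reaches the outcome by a route that perceived risk, worry and previous mammogram do not capture.
2. **Collider bias, mainly for leaflet reading.** The leaflet was linked in the invitation letter, so worry and perceived risk as reported may already reflect having read it. They would then be common effects of reading and of history. Conditioning on them while leaving history out ties reading to history, and any direct effect of history on the outcome then shows up in the odds ratio for reading.

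At stake are the adjusted odds ratios for reading, decision stage and intended participation. These inform the decision-stage analysis and Aims 1 to 3.

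**Working it through.** **Step 1: compare the lists.** Of the four adjacent questionnaire items perceived risk, worry, family/friends history and previous mammogram, the footnote keeps the first, second and fourth and drops the third.

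**Step 2: is there a figure to reproduce?** No. The SAP gives no sample size, expected odds ratio or prevalence of family/friends history for these models, so every input below is an assumption.

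**Step 3: model.** There are 1,000,000 simulated women per scenario. F is family/friends history (prevalence 10%, 30% or 50%), X a binary exposure, W worry, R perceived risk and Y the outcome.

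- logit P(X=1) = a·F
- W = s·F + t·X + N(0,1)
- R = s·F + N(0,1)
- logit P(Y=1) = 1.0 + 0.3·W + 0.3·R + d·F

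X is absent from the last line, so its true odds ratio given W, R and F is 1.00. Previous mammogram is not modelled.

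**Step 4: scenarios.**

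- A: F acts on Y only through W and R; exp(a) = 1.5, s = 0.8, t = 0, d = 0.
- B: direct effect; exp(a) = exp(d) = 1.5, s = 0.8, t = 0.
- B2: as B, with both odds ratios 2.
- C: collider; a = 0, s = 0.8, t = 0.5, exp(d) = 2.
- C2: stronger collider; a = 0, s = 1, t = 1, exp(d) = 2.
- D: randomised exposure with no effect on worry; a = 0, s = 0.8, t = 0, exp(d) = 2.

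**Step 5: results.** Odds ratio for X at F prevalence 10% / 30% / 50%.

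| Scenario | Adjusted for W, R | Adjusted for W, R, F | Ratio of the two |
|---|---|---|---|
| A | 1.000 / 1.000 / 1.001 | 1.000 / 1.000 / 1.000 | 1.00 / 1.00 / 1.00 |
| B | 0.997 / 1.023 / 1.027 | 0.987 / 1.000 / 0.995 | 1.01 / 1.02 / 1.03 |
| B2 | 1.021 / 1.069 / 1.092 | 0.995 / 1.003 / 1.002 | 1.03 / 1.07 / 1.09 |
| C | 0.979 / 0.971 / 0.941 | 0.995 / 1.008 / 0.989 | 0.98 / 0.96 / 0.95 |
| C2 | 0.962 / 0.921 / 0.894 | 0.995 / 1.000 / 1.000 | 0.97 / 0.92 / 0.89 |
| D | 0.992 / 1.004 / 0.997 | 0.991 / 1.004 / 0.997 | 1.00 / 1.00 / 1.00 |

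The fits that include F should give exactly 1.00. They miss by at most 0.013 (1.000 − 0.987), so simulation noise is about 1%. The last column, for example 1.092/1.002 = 1.09, shows the effect of the omission with most of that noise removed.

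**Step 6: reading the table.** Confounding gives 0-9% upward (0.997 to 1.092) and the collider path 2-11% downward (0.979 to 0.894). Adding F removes both, within noise. There is no bias in A, nor in D. The signs follow from the assumption that history and exposure both push worry upward and that history raises participation. If reading lowered worry, the collider bias would point the other way.

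**The case against.** The strongest reply is that the footnote already adjusts for the main routes by which knowing someone with breast cancer would shape screening attitudes. If those routes are the whole story, nothing is left to confound, as scenario A shows. This stands. A reader might infer that the adjusted odds ratios are confounded as a matter of fact, but the SAP does not support that. It shows only that they may be, because it gives no basis either for or against a direct effect.

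Other objections also stand, in part or in full.

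- **Size.** A reader might model worry as the only adjusted risk variable. With 40% reading, 75% intending, 30-50% with history, and history odds ratios of 1.5-2 with reading, 2-3 with worry and 1.5-3 with intention, the reading odds ratio is then 1.03-1.19. That is not the planned model, because perceived risk and previous mammogram are also in the list. The range should not be used.
- **Not the only upstream item.** A reader might take family/friends history to be the one collected factor that lies before perceived risk, worry and previous mammogram. Previous breast cancer is also collected and also omitted. Adding family/friends history therefore does not guarantee complete adjustment; in the simulation it does so only because no other common cause was put in.
- **The collider path is narrow.** It needs the exposure to change worry or perceived risk, and that mechanism is plausible mainly for leaflet reading. If reading does change worry, adjusting for worry also removes part of the effect of reading. In scenario C2, adjusting for F alone gives 1.33-1.34, while W, R and F together give 1.00. Adding the item closes the path through history but does not settle whether a post-exposure variable belongs in the model.
- **Purpose.** The SAP does not say that the adjusted odds ratios are causal. However, it uses them to examine statements such as whether women take information into account, and it reports them beside crude estimates, so a better adjustment set is still useful.
- **Reach.** The main-hypothesis prevalences, the chi-squared comparison of framings and the regression of intended participation on framing do not depend on this item. Scenario D agrees, provided framing does not itself alter worry.

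None of this shows that leaving the item out is preferable.

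**Conclusion.** The point holds as a minor one. One collected, pre-exposure item is missing without explanation from the only covariate list. In models where the exposure is not randomised, the adjusted odds ratio may therefore carry residual bias. The condition is that family/friends history affects the outcome outside the adjusted variables, and that it is either associated with the exposure or shares worry or perceived risk with it as a common effect.

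The quoted shifts rest wholly on assumed inputs: direct odds ratios of 1.5-2, shifts in worry of 0.5-1 residual SD and prevalences of 10-50%. The SAP does not say where in that range the study lies, or in which direction the bias would run. Previous mammogram was left out of the simulation, so whatever part of the assumed direct effect it carries would shrink these figures. The study's main-hypothesis prevalences and its randomised comparison stand as planned.

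**What to change.** Add breast cancer among family/friends to the covariates in the single-asterisk footnote, for adjusted models whose exposure is not randomised: reading information, decision stage and intended participation. If the sponsor prefers to leave it out, state the reason in the footnote and report a sensitivity analysis that includes it.

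The cost is one phrase in the footnote and one or two extra parameters per model. No new data are needed, and the planned prevalence estimates and the chi-squared test do not change.

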More/less willing: Focus is on women being less willing to participate, therefore, the two “less willing” responses will be coded as 1 and the two “more willing” responses and “unchanged” will be coded as 0.

If our hypothesis is not true, the dichotomization will be reversed (“unchanged” will still be coded 0).

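### The outcome coding for the two Aim 1 change items is chosen from the results by an undefined rule, and change in the other direction is never modelled

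*SAP*

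**What the plan says.** Under Aim 1, in the subsections on being more or less positive/negative and on being more or less willing to participate, the SAP notes for each item: "Dichotomization of outcome depends on results". Each item has one binary outcome for its crude and adjusted models. For the first this is "logistic regression with more or less positive/negative as outcome and intended participation and framing as categorical independent variables", and for the second "logistic regression with more/less willing as outcome and intended participation and framing as categorical independent variables".

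Footnote ** gives the rule. The expectation is stated once for both items: "we hypothesize that it is more likely that women will be more negative and less willing to participate after reading screening information", as opposed to becoming still more positive and willing. Then: "If this hypothesis is true, the responses will be dichotomized as follows". For the first item, "the two “negative” responses will be coded as 1 and the two “positive” responses and “unchanged” will be coded as 0", and the willingness item is treated in the same way. The alternative branch is: "If our hypothesis is not true, the dichotomization will be reversed", with the unchanged response staying at 0.

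The SAP also plans a descriptive analysis covering both directions: "Estimate prevalence of women who are more or less positive/negative depending on previously intended participation and framing, respectively". A matching line covers willingness.

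**The concern.** **The switch has no rule.** Both codings are written out, but not how to decide between them. The SAP does not say whether the hypothesis counts as true on a simple majority or on a significant difference, whether the count is pooled or by group, or which women enter it. Because one hypothesis joins both items, no coding is fixed if women turn out more negative yet more willing.

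**One direction is always left out of the models.** Aim 1 asks whether women take the information into account, and movement either way is evidence that they do. Under either coding, movement in one direction is merged with no movement. A framing or intention effect confined to that direction gets no odds ratio, no adjustment and no test, even if the plan is followed exactly.

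At stake is which odds ratios are estimated for these two items, and whether a real difference in the less common direction would be noticed beyond a descriptive table.

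**Working it through.** The SAP gives no rates, group sizes or significance level for these items, so there is no planned figure to reproduce. Both gaps follow from the wording alone. The figures below show how much they could matter, using assumed rates, a crude two-group z-test and a two-sided 5% level.

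**1. Effect in the unmodelled direction.** Assume negative/unchanged/positive of 10/70/20% (opportunity framing) and 20/60/20% (choice framing). Positives outnumber negatives, so a majority rule reverses the coding and positive = 1.

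- Modelled framing OR: (0.20/0.80)/(0.20/0.80) = 1.00.
- OR for turning negative: (0.20/0.80)/(0.10/0.90) = 2.25.
- Against unchanged: negative (20/60)/(10/70) = 2.33; positive (20/60)/(20/70) = 1.17.

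The third randomised group need not alter the choice. With 10–20% negative and 20% positive in that group, pooled negatives are (10+20+10)/3 = 13% to (10+20+20)/3 = 17%, still below 20%.

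Approximate power of the negative contrast at 500 per group: SE = √(0.15 × 0.85 × 2/500) = 0.0226, z = 0.10/0.0226 = 4.43, power ≈ Φ(4.43 − 1.96) = 0.99. Simulated rejection rates (100,000 draws per scenario):

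| Assumed rates (neg/unch/pos, %) | Per group | Planned coding | Negative contrast |
|---|---|---|---|
| 10/70/20 v 20/60/20 | 500 | 0.052 | 0.994 |
| 12/68/20 v 16/64/20 | 500 | 0.051 | 0.445 |
| 12/68/20 v 16/64/20 | 1000 | 0.049 | 0.734 |

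The milder case has a binary OR of (0.16/0.84)/(0.12/0.88) = 1.40.

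The gap is the same when the SAP's hypothesis holds. With 20/70/10 v 20/60/20, a positive-direction OR of 2.25 goes unmodelled. A separate simulation with 20% negative in both groups and 5% v 10% positive gave about 5% rejection for the planned coding. The positive contrast was rejected in 66%, 99% and about 100% of runs at 300, 1000 and 3000 per group.

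**2. The undefined switch.** Compare two readings of the hypothesis being true: (a) more negatives than positives, (b) significantly more at 5%. For true rates of 15% v 13% and n = 1000 women, the difference in counts has mean 20 and SD √(1000 × (0.28 − 0.02²)) = 16.7, so z = 1.20. The readings conflict with probability about Φ(1.20) − Φ(1.20 − 1.96) = 0.88 − 0.22 = 0.66. Simulation:

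| True rates | n = 500 | n = 1000 | n = 3000 |
|---|---|---|---|
| 15% v 13% | 0.673 | 0.677 | 0.448 |
| 15% v 10% | 0.408 | 0.124 | 0.000 |

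**3. Items pointing in different directions.** With both items at 15% v 13% and n = 1000, they disagree in 12–19% of samples (latent correlation 0.9 down to 0.3). At 15% v 10% and n = 1000, one item points the wrong way in about 0.09% of samples. Even independent items then disagree in only about 2 × 0.09% ≈ 0.2%.

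**4. Type I error.** If pooled counts blind to group decide the coding, the rejection rate under no effect stays at about 5% (0.049–0.051 across the scenarios run). If the coding could be picked after seeing both group contrasts, it is 9.5–9.9%, in line with 1 − 0.95² = 9.75%. The SAP does not say which applies.

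**The case against.** The strongest reply is that this is a prespecified rule with two branches. The footnote names the comparison, writes out both codings item by item, and gives a ceiling argument for focusing on one direction. The natural reading is a simple count among all women, and the significance-based reading used above is not in the SAP. Conflicts between readings or between items are frequent only when the two directions are nearly equal. The 5% v 99% contrast is built in, because the modelled direction was given no effect. The opposite direction would still show in the planned prevalences. A multinomial model with seven adjustment variables plus framing and intended participation could be unstable if one direction is rare.

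Much of this stands. The rates are assumed, the conflicts fade as the directions separate, a pooled count leaves type I error intact, and sparse data are a genuine risk. But the natural reading is not written down, and an item-wise decision is not stated. Nor would defining the switch close the second gap: a clear rule would still leave one direction without a model. The simulated contrast illustrates that consequence and does not predict this study's data.

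**Conclusion.** The concern holds. The regression outcome for both change items depends on the observed results through a criterion with no statistic, population or per-item rule. Whichever branch is taken, differences in the other direction remain descriptive and unadjusted. Under the assumed rates, an odds ratio of 1.40 to 2.25 in that direction could go without any test, although a direct contrast would detect it in 45% to 99% of samples at 500 per group.

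The reach is limited to two supporting items under Aim 1. The other Aim 1 analyses, the main hypothesis and Aims 2 and 3 do not use this switch, and the overall prevalence of change is unaffected. It should be corrected because the gap is avoidable with the data already planned.

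**What to change.** Remove footnote ** as a coding rule. For each item, specify one multinomial logistic regression, crude and adjusted for the existing covariates, with three outcome levels: more negative / unchanged / more positive, and less willing / unchanged / more willing. Use unchanged as the reference and intended participation and framing as categorical predictors. Report both sets of odds ratios with 95% confidence intervals.

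At minimum, prespecify and report both binary codings for each item. This is also a workable fallback if one direction proves too sparse for the adjusted multinomial model. Keep the expected direction as a stated hypothesis that does not determine the coding.

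The cost is a change of SAP wording, with the same data and covariates. The price is one extra set of odds ratios per model and wider, possibly unstable, intervals for the rarer direction.
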